Cubii for Exercise in People With MS

NCT0582643

August 5, 2024

Cubii for Exercise in People With MS

NCT0582643
August 5, 2024

Cubii-MS Study Protocol

Principal Investigator: [name]., University of Washington

1. Background and Specific Aims

Nearly one million people in the United States (U.S.) live with multiple sclerosis (MS),¹ a typically progressive disease that can cause widespread impairment across physical and psychological domains (e.g., mobility impairments, fatigue, pain, anxiety and/or depression, cognitive dysfunction). Unfortunately, there is currently no cure for MS, and the disease often has a significant negative impact on functioning and quality of life.² Some pharmacologic treatments aim to reduce or stop the rate of disease progression, while other pharmacologic and nonpharmacologic interventions focus on improving symptom management and functioning

Data indicates people with MS are less active than their peers in the general population. Exercise interventions are important non-pharmacologic approaches to maximize function and quality of life for people living with MS. Based on current evidence and expert opinion, the National Multiple Sclerosis Society (NMSS) recommends that healthcare providers promote the benefits of exercise and lifestyle physical activity for every person with MS.

Individuals with at least moderate impairment (approximately 50% of the MS population) often require adaptive exercise due to mobility and balance impairments. Typically, these individuals experience limitations in walking distance and present with neurologic impairments that impact their gait and/or coordination. This may necessitate precautions for falls, as well as the use of assistive devices or compensatory strategies. The Cubii product line is well-placed for this subset of the MS population as it allows for safe, seated exercise that can still meet the recommendations for aerobic and resistance training.

To address this need, this study will capitalize on a representative, heterogeneous sample of MS patients who are seeking to change their coping behaviors around MS, including by exercising more, and an existing exercise unit that can be utilized by people with a range of mobility.

The **specific aims** of this prospective observational study are to evaluate
(1) the feasibility, usability, and satisfaction with the Cubii elliptical and
(2) the preliminary efficacy of the Cubii elliptical for increasing activity (primary outcome), physical function, and quality of life, and decreasing physical and psychological symptom (e.g., pain, fatigue, depression) severity in people with MS.

2. Study Design & Methods

To achieve the study aims, we will conduct a prospective observational study that combines self-reported measures and the use of the Cubii exercise unit.

Participation in this study will involve (1) presenting to the UW Medicine Multiple Sclerosis Center (“MS Center”) to complete “baseline” assessments (T1; see section X.X) and receive their Cubii exercise unit; (2) self-directed use of the Cubii exercise unit at home for 8 weeks; and (3) returning to the MS Center to complete a walking test and an assessment (T2).

Study coordinators will maintain a relationship with participants to ensure adherence to the study protocol. This may include contact participants (according to their preferred method) at the midpoint of the self-directed home exercise period to troubleshoot any issues that may have arisen.

Participants will be compensated \$100 for full completion of the study (\$40 for participating at T1 and \$60 after completing the assessments at T2).

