2.1. Study Sample and Recruitment

We will recruit and enroll N = 20 individuals with MS from the MS Center. We will use the existing participant registries (N > 1,500), electronic health record queries, institution-specific subject-recruitment websites, and provider referrals.

Table 1. Study Inclusion and Exclusion Criteria

Inclusion Criteria
1. 18 years of age or older
2. Can fluently converse and read in English (to complete study questionnaires)
3. Clinician-confirmed MS
4. Walks with the aid of an assistive device (e.g., cane, walker, forearm crutches)
5. Lives in the greater Seattle metropolitan area
6. All genders
7. Has an iPhone or Android phone able to download an app
Exclusion Criteria
1. People unable to exercise for health reasons

3. Enrollment and Data Collection Procedures

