3.2. Study Procedures and Materials

Pre-baseline visits tasks Participants will first complete validated self-report questionnaires (demographics, MS disease-related variables (e.g., pain, fatigue, falls), activity, exercise, quality of life, and biopsychosocial symptom variables).

In-person baseline visit

At the baseline visit (T1), participants will come to the MS Center for a 60-minute visit during which they will take a six-minute walking test, and engage with staff for a brief orientation to the Cubii and its phone app.

Eight-week at-home period

Participants will use the Cubii at home for two months. Participants will use the unit as they choose and maintain a log regarding their device use.

In-person post-treatment visit

Participants will return to the UW MS Center at nine weeks and complete the same validated self-report questionnaires at baseline and provide additional data regarding the feasibility, usability, and satisfaction with the use of the Cubii.

Table 2. Study Activities

Primary Outcomes	Domain	Study Activity	Baseline (week 1)	Weeks 2-8	Week 9
		Demographics	X		X
		Medical/Surgical History/Disease variables	X		
		Anticipated experience/use/satisfaction	X		
		Patient Global Impression of Change (PGIC)	X		X
Additional covariates	Satisfaction with social roles	PROMIS Satisfaction with Participation in Social Roles Short Form 8a	X		X
	Self-efficacy	University of Washington Self-Efficacy Scale short form	X		X
	Resilience	UW Resilience Scale 8-item short form v1.0	X		X
	Comorbidities	Comorbidity Questionnaire	X		X

	Physical Activity Readiness scale	PAR-Q+	X		X
Preliminary efficacy	Physical activity	Godin Leisure Time Exercise Questionnaire	X		X
	Physical function	PROMIS Short Form v2.0 - Physical Function 20a	X		X
	Quality of life	MSQOL54- Quality of Life Subscale	X		X
	Pain intensity	PROMIS Pain Intensity Short Form 3a	X		X
	Pain interference	PROMIS Pain Interference Scale (Short Form 8b, V1.0)	X		X
	Fatigue interference	PROMIS SF v1.0 - Fatigue- Multiple Sclerosis 8a	X		X
	Depression	PROMIS Short Form v1.0 Depression 8a	X		X
	Anxiety	PROMIS Short Form v1.0 - Anxiety 8a	X		X
	Ambulatory function	CogDetect walking tests	X		X
	Fatigue intensity	Brief Fatigue Inventory (BFI)	X		X
		Measure of falls	X		X
		Spacitcty	X		X

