5.1. Sample Size Determination

The study sample size ($N = 20$) is consistent with pilot studies that seek to examine feasibility, usability, and satisfaction of an intervention or device, and provides an opportunity to collect preliminary data on efficacy. Consistent with pilot studies in general, this sample size is underpowered to make definitive conclusions about the effect of the device on primary outcomes; in contrast, it is sufficient for serving as the basis for future applications for full-size trials that are sufficiently powered to test such outcomes.

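### Aim 2 is framed as efficacy of the Cubii, but a single-group before-after comparison cannot attribute change to the device, and the only limit the plan states is sample size

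*Combined protocol and SAP*

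**What the plan says.** - **Aim 2 (section 1)** is to evaluate "the preliminary efficacy of the Cubii elliptical for increasing activity (primary outcome), physical function, and quality of life", and also "decreasing physical and psychological symptom (e.g., pain, fatigue, depression) severity in people with MS". This is a directional question about what the device does.
- **Section 2** calls the study prospective and observational. Taking part consists of a baseline visit at which the unit is handed over, "self-directed use of the Cubii exercise unit at home for 8 weeks", and a return visit.
- **Section 2.1** describes one group: "We will recruit and enroll N = 20 individuals with MS from the MS Center". No control, waiting-list or external comparison group appears anywhere.
- **Table 2 (section 3.2)** heads the aim 2 outcomes "Preliminary efficacy". They are marked at baseline and week 9 only. The sole entry in the physical activity domain is the "Godin Leisure Time Exercise Questionnaire".
- **Section 5.1** says that the sample "provides an opportunity to collect preliminary data on efficacy", but that "this sample size is underpowered to make definitive conclusions about the effect of the device on primary outcomes". It adds that N = 20 is enough to support later applications for adequately powered trials.
- **Section 5.2** tests aim 2 by looking for significant within-person change. Its participant-flow list includes a count of those *randomized*, although no allocation is described.

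**The concern.** The aim and the analysis answer different questions. Aim 2 asks whether the Cubii increases activity. Section 5.2 asks whether activity differed between baseline and week 9. The second answers the first only if nothing else would have moved the outcome over those weeks, and the plan neither makes nor defends that assumption.

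The plan's own text suggests other possible sources of change, though it does not name them as such:

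- The background section describes the sample as people already looking to exercise more. This is background text, not an entry criterion.
- Coordinators keep in touch with participants to support adherence. The midpoint contact is optional.
- Activity is self-reported by people who know they have been given an exercise device. This does not apply to the walking tests, but the attribution limit does.

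The stated caveat concerns power alone. A reader of section 5.1 could conclude that size is all that stands between this study and a statement about the device. Because section 5.1 offers the results as a basis for later applications, a before-after change labelled preliminary efficacy could be carried forward as evidence that the device works. Aim 1 (feasibility, usability, satisfaction) is unaffected.

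**Working it through.** **1. Is there a stated figure to reproduce?** No. N = 20 is justified in section 5.1 only as usual for a pilot. The documents give no test, alpha, effect size, SD or expected loss.

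**2. What the schedule allows.** I count 12 rows in the Table 2 block: nine named questionnaires, one walking-test row, and two rows (falls and spasticity) with no domain or instrument named. All 12 are marked at baseline and week 9 only. Placing the last two rows in the block is a reading of an extracted table, and the argument does not depend on them. There is no concurrent comparator and no repeated baseline.

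**3. What the analysis estimates.** Let D be a participant's week 9 value minus baseline, δ the mean effect of the device, and β the mean change that would have occurred without it. Then:

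- expected mean of D = δ + β
- standard error of the mean = SD(D)/√n

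There is one observable quantity and two unknowns. Increasing n shrinks the standard error, but the mean still converges on δ + β, not on δ. Power and attribution are therefore separate limits, and section 5.1 states only the first.

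**4. Illustration.** Everything here is assumed: paired t-test, two-sided alpha 0.05, changes in units of SD(D), and either 20 completers or 16 (20% loss).

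- n = 20: critical t (19 df) = 2.093, so the significance threshold is 2.093/√20 = 0.468 SD. A larger observed mean change is significant whatever its cause.
- n = 16: the threshold is 0.533 SD.

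Three different truths give the same net shift at n = 20 and so the same chance of significance (non-central t):

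| Device δ | Background β | δ + β | Chance of significance |
|---|---|---|---|
| 0.5 | 0 | 0.5 | 56% |
| 0 | 0.5 | 0.5 | 56% |
| 0.8 | -0.3 | 0.5 | 56% |

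With the device effect set to zero:

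| Assumed β (SD) | n = 20 | n = 16 |
|---|---|---|
| 0.2 | 14% | 12% |
| 0.5 | 56% | 46% |
| 0.8 | 92% | 85% |

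These are correct rejections of no change, not false positives. They mislead only if read as a device effect.

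**5. Does any passage state the limit?** I looked for a statement that change cannot be assigned to the Cubii, or that a comparator is missing, and found none. The words pilot, preliminary and observational all appear, but none is tied to the lack of a comparator.

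**The case against.** The plan is already modest. It calls itself an observational pilot, aim 2 says preliminary, section 5.1 disclaims definitive conclusions about the device, and section 5.2 correctly says within-person change. A single group is a reasonable choice for 20 people in a feasibility study. The calculation shows only that a test of change detects change, and nothing in the documents makes a background shift of 0.5 or 0.8 SD more likely than zero.

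Much of this stands. The single-group design is not the fault, no control arm is being asked for, and the rates say nothing about how likely a background shift is in this trial. What does not stand is that the modest wording covers the gap, because section 5.1 rests its caution on size alone.

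A reader might also infer several stronger points that the documents do not support:

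- *That a significant result will count as meeting aim 2.* No passage sets significance as the criterion or says how a positive result will be described. It could be reported as efficacy, but the plan does not say that it will be.
- *That a null result will be taken as no device effect.* The power caveat in section 5.1 already guards against this.
- *That section 5.1 proposes a larger uncontrolled study.* It does not describe the design of the later trials.
- *That the word randomized in section 5.2 implies arms.* Nothing else in the plan describes allocation, so it supplies no comparator.

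The phone app and the device-use log in section 3.2 bear on exposure. No analysis of them is planned, and they would not replace a comparator.

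**Conclusion.** The point holds and should be fixed. Aim 2, the Table 2 label and section 5.1 use the language of efficacy or device effect for a comparison that can show change but not its cause, and the one limit stated is a different one. This conclusion rests on the design as described and needs no assumed figure. The 56% result only illustrates that the planned test cannot tell the three scenarios apart; the test, alpha, background shifts and completer numbers behind it are all assumed. The consequence is confined to how aim 2 results are described and carried into later applications.

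**What to change.** 1. **Aim 2 and Table 2.** Restate aim 2 as estimating change from baseline to week 9, among people given a Cubii, in activity (primary), physical function, quality of life and symptom severity. Relabel the Table 2 block *Change from baseline to week 9*. Expected directions may be kept as hypotheses.
2. **Section 5.1.** Refer to *preliminary data on within-person change* in place of preliminary data on efficacy, and add: *Because there is no comparator, change cannot be attributed to the device at any sample size; N = 20 additionally limits precision.*
3. **Section 5.2.** Report within-person change as an estimate with a 95% confidence interval, state that it will not be interpreted as the device effect, and delete *randomized* from the participant-flow list.

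The cost is a more modest claim: later applications would cite feasibility data and an estimate of within-person change with its SD, not a device effect. No visits, participants or questionnaires are added. Section 6.2.1 says that the IRB has approved the protocol, so I assume a wording amendment would be needed.

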2.1. Study Sample and Recruitment

We will recruit and enroll N = 20 individuals with MS from the MS Center. We will use the existing participant registries (N > 1,500), electronic health record queries, institution-specific subject-recruitment websites, and provider referrals.

Table 1. Study Inclusion and Exclusion Criteria

Inclusion Criteria
1. 18 years of age or older
2. Can fluently converse and read in English (to complete study questionnaires)
3. Clinician-confirmed MS
4. Walks with the aid of an assistive device (e.g., cane, walker, forearm crutches)
5. Lives in the greater Seattle metropolitan area
6. All genders
7. Has an iPhone or Android phone able to download an app
Exclusion Criteria
1. People unable to exercise for health reasons

3. Enrollment and Data Collection Procedures

3.1. Screening

Research staff will reach out to interested participants and provide them with more information about the study and answer their questions. During the initial phone contact, staff will provide a brief overview of the study. If a participant is interested in going through the screening process, research staff will, with the participant’s permission, ask them screening questions to determine eligibility and to obtain basic demographic information (e.g., age, sex, gender, geographic location).

For eligible participants, we will collect additional contact information (e.g., confirm name, email, phone number(s)). Research staff will also document the outcome of the screening and the reason for ineligibility or decline.

3.2. Study Procedures and Materials

Pre-baseline visits tasks Participants will first complete validated self-report questionnaires (demographics, MS disease-related variables (e.g., pain, fatigue, falls), activity, exercise, quality of life, and biopsychosocial symptom variables).

In-person baseline visit

At the baseline visit (T1), participants will come to the MS Center for a 60-minute visit during which they will take a six-minute walking test, and engage with staff for a brief orientation to the Cubii and its phone app.

Eight-week at-home period

Participants will use the Cubii at home for two months. Participants will use the unit as they choose and maintain a log regarding their device use.

In-person post-treatment visit

Participants will return to the UW MS Center at nine weeks and complete the same validated self-report questionnaires at baseline and provide additional data regarding the feasibility, usability, and satisfaction with the use of the Cubii.

Table 2. Study Activities

Primary Outcomes	Domain	Study Activity	Baseline (week 1)	Weeks 2-8	Week 9
		Demographics	X		X
		Medical/Surgical History/Disease variables	X		
		Anticipated experience/use/satisfaction	X		
		Patient Global Impression of Change (PGIC)	X		X
Additional covariates	Satisfaction with social roles	PROMIS Satisfaction with Participation in Social Roles Short Form 8a	X		X
	Self-efficacy	University of Washington Self-Efficacy Scale short form	X		X
	Resilience	UW Resilience Scale 8-item short form v1.0	X		X
	Comorbidities	Comorbidity Questionnaire	X		X

	Physical Activity Readiness scale	PAR-Q+	X		X
Preliminary efficacy	Physical activity	Godin Leisure Time Exercise Questionnaire	X		X
	Physical function	PROMIS Short Form v2.0 - Physical Function 20a	X		X
	Quality of life	MSQOL54- Quality of Life Subscale	X		X
	Pain intensity	PROMIS Pain Intensity Short Form 3a	X		X
	Pain interference	PROMIS Pain Interference Scale (Short Form 8b, V1.0)	X		X
	Fatigue interference	PROMIS SF v1.0 - Fatigue- Multiple Sclerosis 8a	X		X
	Depression	PROMIS Short Form v1.0 Depression 8a	X		X
	Anxiety	PROMIS Short Form v1.0 - Anxiety 8a	X		X
	Ambulatory function	CogDetect walking tests	X		X
	Fatigue intensity	Brief Fatigue Inventory (BFI)	X		X
		Measure of falls	X		X
		Spacitcty	X		X

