3.3. Data Collection Technology

We will collect survey data via a secure REDCap website. REDCap is an open-source, secure, HIPAA-compliant web-based platform designed to support data capture for research studies. Vanderbilt University designed it to protect patient privacy and confidentiality while assisting investigators in clinical research. It provides an interface for data entry and validation, auditing features for tracking data manipulation, the ability to import data from external sources, calculated data fields, branching logic, and the capability to export data to many statistical packages. System and application-level security include SSL encryption of internet traffic (https pages), hosting in a secure data center with nightly backup, fine-grained control over user rights, detailed audit trails, record locking, and de-identification features for data export.

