3.4.1. Self-Report Measures

The participants will complete online self-report surveys via REDCap. Study staff will register participants in REDCap and provide a participant-specific URL to access the surveys. The survey battery will take approximately 20 minutes and study staff will be available to assist as needed. See above table for measures and participant demographics and clinical characteristics: demographic questions (age, sex, gender, race, ethnicity, education, income, marital status,

employment status & healthcare coverage), clinical survey (e.g., time since diagnosis, MS subtype, brief medical and psychiatric history, and other clinical characteristics), and treatment survey (e.g., medications and therapies).

Ambulatory measures

Motor Function: We will administer a 4-m backward walking test, evaluation of gait speed (4 meter walk test), and gait endurance (2-minute walk test).

Backward gait speed: Backward walking is used to assess balance and fall risk. Participants walk backwards a short distance at their usual pace, completing one practice and two-timed trials. Scores are recorded as time in seconds required to walk 4 meters on each of two trials, with the better trial used for scoring. The test time is ~3 minutes.

Gait speed: The 4-meter walking test measures locomotion. Participants walk a short distance at their usual pace, completing one practice and two-timed trials. Scores are recorded as time in seconds required to walk 4 meters on each of two trials, with the better trial used for scoring. The test time is ~3 minutes.

Gait endurance (2-minute walk test): This test assesses the ability to sustain effort that requires conjoint work capacities from cardiopulmonary function, biomechanical, and neuromuscular function. The test time is ~4 minutes.

4. Data Management: Storage and Sharing

We will use REDCap to collect and store study data and participant identifiers. We will (1) assign each participant an ID number in REDCap to maintain confidentiality and (2) use this ID number to code/label study data. The link between the study data and a participant's identity will only exist in REDCap, to which only research staff members have access.

We will label any paper forms only with the ID number and keep them in a locked cabinet separate from any identifying information and will scan and upload them to REDCap as a source document.

We will track protocol deviations and adverse events in REDCap.

5. Data Analysis/Statistical Methods

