10.2. Unanticipated Problems and Protocol Deviation Reporting

Regulations require investigators to report unanticipated problems involving risks to participants or others, as well as any other event or information that may increase risks, may alter the risk-benefit assessment, may affect the participant's willingness to participate in the research, or may represent a departure from applicable human subject protections regulations or policies (i.e., a protocol deviation).

We will report all instances to the IRB with the following exceptions:

1. Participants who skip study assessments
2. Participants who decline the participant payment. It has been our experience that some research participants do not wish to receive payment for their participation in their study

11. Quality Control Procedures

Cubii staff will train the study staff on the unit as outlined in the Manual of Procedures (MOP). Managers will monitor staff throughout the course of the study through regular team meetings.

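### Week-9 questionnaires and the only post-use usability and satisfaction ratings are placed at the return visit, and the existing online link is not assigned to participants who miss it

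*Combined protocol and SAP*

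**What the plan says.** **Where week-9 data are collected.** Section 2 describes T2 as a return to the MS Center for a walking test and an assessment. Section 3.2, under the in-person post-treatment visit, states: "Participants will return to the UW MS Center at nine weeks and complete the same validated self-report questionnaires at baseline". The same sentence has them "provide additional data regarding the feasibility, usability, and satisfaction with the use of the Cubii". No other section plans ratings after use. Table 2, as far as its layout can be read, lists only "Anticipated experience/use/satisfaction", marked at baseline.

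**Activity.** Activity is the primary outcome of aim 2. Its questionnaire in Table 2 is the "Godin Leisure Time Exercise Questionnaire", marked at baseline and week 9, with nothing in weeks 2-8.

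**How surveys are delivered.** Section 3.3: "We will collect survey data via a secure REDCap website". Section 3.4.1, under the lab-visit heading: "Study staff will register participants in REDCap and provide a participant-specific URL to access the surveys". Section 3.2 also has the self-report questionnaires completed before the in-person baseline visit.

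**What happens when data are missing.** Section 9 plans an exit attempt and a recorded reason for those who withdraw or are lost, without naming an exit survey. Section 10.2 lists "Participants who skip study assessments" among the events not reported to the IRB. Section 5.2 will report how many enrolled and how many gave data at each time point. For aim 1 it plans descriptive summaries and frequencies, without naming a denominator.

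**The concern.** Section 5.1 justifies 20 participants as suitable for examining feasibility, usability and satisfaction, and offers the results as support for later applications for larger trials. Those ratings come from one sentence about one visit. A participant who keeps the device, stops using it and does not come back remains in the study, yet no section directs staff to ask for that person's opinion, although the means to ask is already in place.

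The people whose ratings are lost may differ from those who return. Someone who disliked the device has less reason to come back. If that happens, satisfaction among attenders overstates satisfaction among recipients. The activity and function results could be affected by a separate route: everyone enrolled walks with an assistive device (Table 1), and a person whose mobility worsens may find the visit harder. Either pattern would pass into the planning of the next trial.

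**Working it through.** The plan has no figure to reproduce here: the sample size rests on pilot convention, and no attrition rate, satisfaction rate or satisfaction cut-off is stated. The only input from the documents is N = 20 (Sections 2.1 and 5.1), taking all 20 to receive a device. Every other rate below is an assumption.

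**1. What is known about a non-attender.**

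| Source | What it gives | Usability or satisfaction rating? | Week-9 Godin score? |
|---|---|---|---|
| Use log (3.2) | Device use, one part of feasibility | No | No |
| Possible midpoint contact (2) | Troubleshooting | None named | No |
| Instruction to report negative experiences (6.2.2) | Problems the participant raises | No | No |
| Exit attempt (9) | Reason for discontinuation | No | No |
| REDCap link (3.3, 3.4.1) | Could give both | Not assigned to non-attenders | Not assigned to non-attenders |

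**2. Bounds on satisfaction over all 20.** With m missing and s satisfied among the 20 − m who respond, the worst case is s/20 and the best is (s + m)/20, so the width is m/20 whatever s is: 1 missing gives 5 points, 3 give 15, 5 give 25. With m = 3:

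| Observed | Worst (s/20) | Best ((s + 3)/20) |
|---|---|---|
| 15/17 = 88% | 75% | 90% |
| 12/17 = 71% | 60% | 75% |
| 8/17 = 47% | 40% | 55% |

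**3. Effect of selective return.** Let q be true satisfaction, and a and b the return probabilities of satisfied and dissatisfied participants. The share seen among attenders is qa / (qa + (1 − q)b). With q = 0.70:

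- a = b = 0.85: 0.595/0.850 = 70%, no shift.
- a = 0.95, b = 0.70: 0.665/0.875 = 76%, 6 points too high.
- a = 0.80, b = 0.95: 0.560/0.845 = 66%, 4 points too low.

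Stronger selection gives more. With a = 0.95, q from 0.50 to 0.70 and b from 0.75 down to 0.50, the shift runs from +4.7 points (0.665/0.890 = 74.7% against 70%) to +15.5 points (0.475/0.725 = 65.5% against 50%).

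**4. Effect on mean activity change.** With 3 missing whose change is k times the attenders' mean, the mean over 20 is (17 + 3k)/20 of the attender mean: 77.5% for k = −0.5, 85% for k = 0, 92.5% for k = 0.5, 100% for k = 1, and 107.5% for k = 1.5.

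**5. Scale against sampling error.** The exact (Clopper-Pearson) 95% interval for 12/17 is 44% to 90%. It is wider than every shift above, but it does not allow for selective return.

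**6. What the link could recover.** If 3 people miss the visit, the 15-point width falls to 5 points if 2 of them answer online and to 10 if 1 answers. It stays at 15 if none answers.

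**The case against.** The strongest reply is that the link already solves the problem. The questionnaires are online and personal to each participant. Section 3.2 has the same set done before the baseline visit, although Section 2 describes baseline assessments as done at the Center. Wording that places an assessment at the Center therefore does not reliably mean that surveys are filled in on site. This stands in part. A reader might infer that the plan forbids remote completion, and the documents do not support that. What remains is that staff have no instruction to send the link to someone who misses week 9.

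A second reply is that loss will be neither silent nor unaddressed. The log, the reports of negative experiences and the recorded reasons can reveal non-use or dislike. Coordinator contact, local residence and the $60 paid after T2 should limit loss. Section 5.2 reports enough counts for a reader to rebuild a denominator and compute the bounds. This also stands. Naming the denominator is therefore a clarification, and formal bounds or shift scenarios in the report are optional. None of these measures supplies the missing ratings or activity scores.

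A third reply is that any shift is assumed and small beside the sampling error of a pilot of 20 that Section 5.1 itself calls underpowered. That is fair on size, and it is why the point concerns how a descriptive result is read.

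**Conclusion.** The gap is real and modest. Post-use ratings and the week-9 activity score are planned at the return visit, and no section assigns the available remote route to those who do not attend. Attender-only satisfaction would be too favourable if people who dislike or stop using the device return less often. It would be unbiased if return is unrelated to outcome, and too low under the reverse pattern. The documents do not show which applies. The firm statement on size is 5 points of worst-to-best range per missing rating, given 20 recipients; the other figures are illustrations.

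Two stronger inferences are not supported. One is that the reported results will be inflated: no attrition figure or pattern is given. The other is that worsening mobility would make satisfaction look too good. Section 1 presents the device as seated exercise suited to people with mobility limits, and nothing links worse mobility to a lower rating. That route bears on the activity and function results only.

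**What to change.** In Section 3.2, send the week-9 questionnaires and the usability and satisfaction survey through the existing REDCap link to every device recipient who has not withdrawn consent to contact. Include those who stopped using the unit and those who cannot attend. Keep only the walking tests tied to the visit.

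In Section 5.2, give the aim 1 usability and satisfaction results with the number responding out of all device recipients beside the observed-case figure.

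The cost is protocol wording, an invitation setting and a few table entries. Remote responders get less in-room help, so record whether each survey was completed in person or remotely. The benefit is not guaranteed: people who dislike the device may also ignore the link.
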